## 7 ASSESSMENT OF SAFETY

### 7.1 Definition of Adverse Events

The International Conference on Harmonisation (ICH) Guideline for Good Clinical Practice (GCP) E6(R1) defines an AE as:

Any untoward medical occurrence in a patient or clinical investigation subject administered a pharmaceutical product and which does not necessarily have a causal relationship with this treatment. An AE can therefore be any unfavorable and unintended sign (including an abnormal laboratory finding), symptom, or disease temporally associated with the use of a medicinal product, whether or not considered related to the medicinal product.

An AE includes but is not limited to any clinically significant worsening of a subject's pre-existing condition. An abnormal laboratory finding (including ECG finding) that requires medical intervention by the investigator, or a finding judged by the investigator as medically significant should be reported as an AE. If clinical sequelae are associated with a laboratory abnormality, the diagnosis or medical condition should be reported (eg, renal failure, hematuria) not the laboratory abnormality (eg, elevated creatinine, urine RBC increased). Abnormal laboratory values that are not, in the investigator's opinion, medically significant and do not require intervention should not be reported as AEs.

AEs may be treatment emergent (ie, occurring after initial receipt of investigational product) or nontreatment emergent. A nontreatment-emergent AE is any new sign or symptom,

disease, or other untoward medical event that begins after written informed consent has been obtained but before the subject has received investigational product.

Elective treatment or surgery or preplanned treatment or surgery (that was scheduled prior to the subject being enrolled into the study) for a documented pre-existing condition that did not worsen from baseline is not considered an AE (serious or nonserious). An untoward medical event occurring during the prescheduled elective procedure or routinely scheduled treatment should be recorded as an AE or serious adverse event (SAE).

## 7.2 Definition of Serious Adverse Events

An SAE is any AE that:

- Results in death
- Is immediately life-threatening
- Requires inpatient hospitalization or prolongation of existing hospitalization
- Results in persistent or significant disability/incapacity
- Is a congenital anomaly/birth defect in offspring of the subject
- Is an important medical event that may jeopardize the subject or may require medical intervention to prevent one of the outcomes listed above

Medical or scientific judgment should be exercised in deciding whether expedited reporting is appropriate in this situation. Examples of medically important events are intensive treatment in an emergency room or at home for allergic bronchospasm, blood dyscrasias, or convulsions that do not result in hospitalizations; or development of drug dependency or drug abuse.

## 7.3 Definition of Adverse Events of Special Interest

An AESI is one of scientific and medical interest specific to understanding of the Investigational Product and may require close monitoring and rapid communication by the investigator to the sponsor. An AESI may be serious or non-serious. The rapid reporting of AESIs allows ongoing surveillance of these events in order to characterize and understand them in association with the use of this investigational product.

Hepatic function abnormality meeting the definition of Hy's law is considered an AESI. See Section 7.6.2 for the definition and reporting of AESIs of hepatic function abnormality.

### 7.3.1 Capillary Leak Syndrome

CLS is a rare and life-threatening condition that can be characterized by capillary hyperpermeability resulting in a shift of intravascular fluid and protein to the interstitial space resulting in transient shock and generalized or segmental edema accompanied by hypotension, elevated hematocrit, and hypoalbuminemia. The systemic CLS may be difficult to recognize and diagnose on initial presentation. A characteristic triad of hypotension, hemoconcentration (elevated hematocrit, leukocytosis, and thrombocytosis), and hypoalbuminemia in the absence of secondary causes of shock is typical. Although CLS has no pathognomonic marker, it should be considered in any patient with acute, severe hypotension, without obvious cardiac dysfunction - particularly if it is unresponsive to or worsens despite aggressive IV fluid resuscitation or vasopressor support and is accompanied by an elevated hematocrit. Treatment of the acute phase is generally supportive, focusing on adequate but not overzealous fluid resuscitation ([Druey and Greipp, 2010](#)). The references are provided as guidance only. Management of the subjects is ultimately at the PI's or designee's discretion.

The sponsor recommends that any subject with any Grade 2 weight change, decrease in albumin (> 1 mg/dL), hypotension, peripheral edema, hypoxia or pulmonary AEs be thoroughly evaluated for other signs and symptoms consistent with CLS. Monitoring for the development of CLS, as well as instructions for supportive care in the event of CLS are outlined in Section 5.2.2.4.

CLS should be suspected if any of the following are observed:

1. A requirement for fluids in excess of 20 mL/kg/hour to treat hypotension.
2. Grade 3 hypotension in temporal association with CLS.
3. Symptomatic pulmonary edema requiring supplemental oxygen or > 10% (absolute) decrease in oxygen saturation in the absence of another clinical explanation.

[REDACTED]

Any changes in body weight must be reported by the subject or caregiver to the staff at the site so the subject can be monitored closely for any other signs/symptoms suggestive of CLS or HUS. PIs should consider inpatient hospitalization for subjects who show signs or have symptoms of CLS.

If subjects develop any grade of CLS during study treatment, [REDACTED]

[REDACTED]  
[REDACTED]  
[REDACTED]  
[REDACTED] a disease assessment including bone marrow examination is encouraged, but not mandatory.

Instructions to the site on how to record (in the eCRF) and report these events (to MedImmune Patient Safety) are provided in Section 7.4.3 and Section 7.6.4, respectively.

### 7.3.2 Thrombotic Microangiopathy/Hemolytic Uremic Syndrome

Thrombotic microangiopathy/HUS is characterized by the triad of microangiopathic hemolytic anemia, thrombocytopenia, and progressive renal failure. Patients also may develop various combinations of pulmonary edema, systemic arterial hypertension, neurologic dysfunction, and cardiac abnormalities ([Corrigan and Boineau, 2001](#); [Banerjee et al, 2009](#)).

If HUS is suspected, the PI or designee will monitor the subject to confirm or rule out a diagnosis of HUS. Subjects with Grade 2 or higher HUS will be admitted for inpatient management.

HUS will be graded using the following expanded guidelines:

Grade 1: Evidence of RBC destruction, without clinical consequences:

- The appearance of schistocytosis ( $\geq 5$ /high power field [HPF]) in a subject with no schistocytosis at baseline, or an increase in the frequency of schistocytes ( $\geq 5$ /HPF) over baseline.

Grade 2: Laboratory findings without clinical consequences:

- Microangiopathic anemia (schistocytosis as defined for Grade 1, and decreased Hgb by 1 g/dL), and
- Mild renal insufficiency (increased creatinine, Grade 1).

Grade 3: Laboratory findings with clinical consequences (eg, renal insufficiency, petechiae):

- Microangiopathic anemia (schistocytosis as defined for Grade 1, and decreased Hgb by 1 g/dL), and/either:
- Grade 4 Thrombocytopenia if platelets were normal at baseline; or

- Moderate renal insufficiency (increased creatinine, Grade 2 if normal at baseline or 1 grade worse than baseline).

Grade 4: Laboratory findings with life-threatening or disabling consequences (eg, CNS hemorrhage/bleeding, or thrombosis/embolism, or renal failure) laboratory findings:

- Microangiopathic anemia (schistocytosis as defined for Grade 1, and decreased Hgb by 1 g/dL), and/either:
- Thrombocytopenia (Grade 4, if platelets were normal at baseline), or
- Moderate renal insufficiency (increased creatinine, Grade 3 if normal at baseline or 2 grades worse than baseline).

Subjects meeting all of the above criteria for Grade 2-4 HUS except for the requirement  $\geq 5$  schistocytes/HPF will be defined as having an “HUS-like event”. Subjects experiencing an HUS-like event should be managed and reported using the same guidelines as for subjects meeting all criteria for HUS.

Any subject with Grade 1-4 HUS or Grade 2-4 HUS-like event will be evaluated with serial haptoglobin, LDH, CBCs, peripheral smear, and urinalyses. Peripheral blood smears will be used to assess for schistocytes. Subjects need not be managed with plasmapheresis, and rather may be managed with fluid repletion and/or diuretics and other supportive measures at the discretion of the PI or designee. Diuresis early on may worsen the creatinine by causing dehydration, and should only be used to treat symptoms of fluid overload. Subjects should be observed carefully for evidence of severe HUS, including mental status abnormalities, renal failure, and bleeding from severe thrombocytopenia. For additional management, PIs or designee may refer to the following publications: [Ariceta et al, 2009](#) and [Michael et al, 2009](#).

If subjects develop any grade of HUS during study treatment, [REDACTED]

[REDACTED]  
[REDACTED]  
[REDACTED]  
[REDACTED] a disease assessment including bone marrow examination is encouraged, but not mandatory.

[REDACTED]  
[REDACTED]  
[REDACTED]

Instructions to the site on how to record (in the eCRF) and report this event (to MedImmune Patient Safety) are provided in Section 7.4.3 and Section 7.6.4, respectively. Each reported

event of thrombotic microangiopathy/HUS of Grade 3 or greater will be followed by the PIs or designees and evaluated by the sponsor. [REDACTED]

### 7.3.3 Ocular Events

Ocular events of special interest to the sponsor are defined as any clinically significant change in vision, retinal abnormalities, or choroidal disturbance that occurs during the course of the study. Subjects will be queried for ocular symptoms at screening, prior to initiation of a new treatment cycle, prior to administration of each moxetumomab dose, and at the end of treatment.

In the event of visual symptoms  $\geq$  Grade 2, ophthalmologic evaluation is required. If a subject has an ocular event with new abnormality by ophthalmologic examination during study treatment, PK and immunogenicity samples, and serum complement factors and serum Ig levels will be collected within 24 hours of diagnosis, during the event as clinically indicated (eg, in order to capture peak intensity of event as well as at least one time point during period of improvement), and after resolution of the event.

Due to the potential association of HUS with retinal damage, subjects should be hospitalized with daily monitoring of renal function with serum creatinine and close observation. If the subject displays any retinal abnormalities, dosing with the investigational agent must be permanently discontinued.

In the event of an ocular event or symptoms occur without any evidence of retinal abnormalities, dosing must be interrupted and may not resume until there is full resolution of ocular symptoms.

In the event of an ocular event where the etiology is unknown, timely follow-up investigations and inquiries must be initiated by the investigational site, based on medical judgment, to make an informed decision regarding the etiology of the event. Ocular events will be followed to resolution until the end of subject participation in the study. Prompt notification of the sponsor is required as with other AESIs.

[REDACTED]

Instructions to the site on how to record (in the eCRF) and report these events (to MedImmune Patient Safety) are provided in Section 7.4.3 and Section 7.6.4, respectively.

## 7.4 Recording of Adverse Events

AEs will be recorded on the eCRF using a recognized medical term or diagnosis that accurately reflects the event. AEs will be assessed by the investigator for severity, relationship to the investigational product, possible etiologies, and whether the event meets criteria of an SAE and therefore requires immediate notification to MedImmune Patient Safety. See Section 7.2 for the definition of SAEs and Appendix 4 for guidelines for assessment of severity and relationship. If an AE evolves into a condition that meets the regulatory definition of “serious,” it will be reported on the SAE Report Form.

Infusion of biological products is commonly associated with infusion related reactions. Anaphylaxis and infusion related reactions have some common manifestations and may be difficult to distinguish from each other. Infusion related reactions are commonly observed during or shortly after the first time exposure to therapeutic monoclonal antibodies delivered through IV infusion. These reactions are less common following subsequent exposures. Unlike infusion related reactions, anaphylaxis is a rare event, usually occurring after subsequent exposure to an antigen, and it is most commonly accompanied by severe systemic skin and or mucosal reactions. The Investigator is advised to carefully examine symptoms of adverse reactions observed during or shortly after exposure to moxetumomab pasudotox, and consider the above mentioned facts prior to making a final diagnosis. Reactions occurring at the time of or shortly after subsequent infusions of investigational product are to be judged by the investigator at his/her own discretion. For the Investigator’s convenience and in order to facilitate consistency in judgments a copy of the National Institute of Allergy and Infectious Diseases (NIAID) and Food and Allergy Anaphylaxis Network (FAAN) guidance for anaphylaxis diagnosis is provided in Appendix 5.

### 7.4.1 Time Period for Collection of Adverse Events

All AEs and SAEs will be recorded from the time of informed consent. AEs will be collected within 4 weeks prior to treatment enrollment, throughout the treatment period, and 4-6 weeks after the last dose (end of treatment).

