### 3.3.4 Tests in Follow-up After Treatment Ends:

#### 3.3.4.1 All patients 28-42 days after the first day of dosing of prior cycle (end of treatment assessment)

- History and physical exam, concurrent medications, AEs, performance status (ECOG)
- Pulse Oximetry with vital signs and weight
- Ophthalmologic exam (slit lamp and fundus)
- 12-lead ECG (analyzed by central vendor, ERT)
- Imaging with CT or MRI for lymphadenopathy and organomegaly
- Bone marrow biopsy and aspirate with flow cytometry/sequencing
- CBC with differential (no peripheral blood smear)
- Chem 7 (sodium, potassium, chloride, bicarbonate, glucose, BUN, creatinine)
- mineral panel (calcium, magnesium, phosphorus, albumin)
- Hepatic panel (AST-SGPT, ALT-SGOT, total bilirubin, direct bilirubin, alkaline phosphatase)
- Uric acid, total protein, triglycerides, cholesterol, GGT
- PT, PTT, LDH, fibrinogen, quantitative immunoglobulins, CK, CRP, serum ferritin

- TSH, fT4, serum amylase, serum lipase, haptoglobin, and urinalysis
- [REDACTED]
- [REDACTED]
- [REDACTED]
- Patients with SD, PR or CR are then followed until relapse from baseline

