#### 5.1.1 Moxetumomab pasudotox

Moxetumomab pasudotox (40 µg/kg) will be administered by IV infusion over 30 (± 10) minutes on Days 1, 3 and 5 of each 28-day cycle until documentation of CR or for up to 6 cycles, progressive disease (PD), initiation of alternate therapy or unacceptable toxicity. The cycle interval can be decreased by up to 2 days. For a dosing delay, refer to Section 6. Subjects will receive up to 6 cycles of therapy.

In an attempt to prevent renal insufficiency, patients will receive fluid and aspirin prophylaxis. Patients will receive low-dose aspirin orally (81 mg daily or local standard dose)

on Days 1-8 of those cycles with platelet counts  $\geq 100 \times 10^9/L$ . Aspirin will be held on days where the platelet count is below  $75 \times 10^9/L$ . Patients will receive 1 L of 5% dextrose 0.45% NaCl, (recommended over 2-4 hours) prior to the beginning and after the end of each moxetumomab pasudotox infusion. Patients under 50 kg may receive 0.5 L instead of 1 L of fluid before the beginning and after the end of moxetumomab pasudotox infusion. On Days 0-8 of the cycle, patients are expected to drink at least 3 liters of fluid/day.

To mitigate risk for allergic reaction and fever, patients will be premedicated with 10- 25 mg hydroxyzine (dose to be determined by the investigator), 650 mg of acetaminophen, and 150 mg ranitidine orally 30-90 minutes prior to every moxetumomab pasudotox infusion. After the end of infusion, patients are recommended to receive acetaminophen 650 mg orally every 6 hours x 4 doses and hydroxyzine 10-25 mg orally every 8 hours for 2 doses. Substitutions of diphenhydramine for hydroxyzine and famotidine or cimetidine for ranitidine are permitted. In subjects experiencing infusion-related reactions, including, but not limited to pyrexia, nausea, or dyspnea, premedication with dexamethasone 4 mg intravenous (IV) or oral may be administered at the investigator's discretion as secondary prophylaxis.

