## **7.4.2 Follow-up of Unresolved Adverse Events**

Any AEs that are unresolved at the subject's last AE assessment or other assessment/visit as appropriate in the study are followed up by the investigator for as long as medically indicated, but without further recording in the eCRF. MedImmune retains the right to request additional information for any subject with ongoing AE(s)/SAE(s) at the end of the study, if judged necessary.

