**Table 10-2 Study Calendar for End of Treatment and Follow-up**

Evaluation/Intervention	EOT a	From end of treatment assessment					Yearly Thereafter (± 1M)
		Every month for 6 months (if in CR) (± 1W)	Every 3 months for 24 months (± 2W)	181D (+ 2W)	12 months (± 1M)	18 months (± 1M)	
History and Physical exam	X			X	X	X	X
Vital signs including pulse oximetry and weight	X			X	X	X	X
Performance Status	X			X	X	X	X
Concurrent medications	X			X	X b	X b	X b
Adverse events	X						
Ophthalmologic exam	X						
12-lead ECG (analyzed by central vendor ERT)	X						
Imaging with CT or MRI of abdomen c	X			X		X	
BM biopsy and aspirate (flow cytometry/sequencing)	X			X d			
Clinical response assessment			X		X	X	X
CBC with differential (no peripheral blood smear)	X	X e	X e	X	X	X	X
Chem 7 (sodium, potassium, chloride, bicarbonate, glucose, BUN, creatinine)	X			X	X	X	X
Mineral panel (calcium, magnesium, phosphorous, albumin)	X			X	X	X	X
Hepatic panel (AST, ALT, total bilirubin, direct bilirubin, AlkPhos)	X			X	X	X	X
Uric acid, LDH, total protein, triglycerides, cholesterol, GGT, PT, PTT, fibrinogen, quantitative immunoglobulins, CK, CRP, serum ferritin	X			X			
TSH, fT4, serum amylase, serum lipase, haptoglobin, urinalysis	X			X			
████████████████████	█						

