**Table 10-2 Study Calendar for End of Treatment and Follow-up**

Evaluation/Intervention	EOT a	From end of treatment assessment					Yearly Thereafter (± 1M)
		Every month for 6 months (if in CR) (± 1W)	Every 3 months for 24 months (± 2W)	181D (+ 2W)	12 months (± 1M)	18 months (± 1M)	
[REDACTED]	■			■	■	■	■
[REDACTED]	■			■			

AlkPhos = alkaline phosphatase; ALT = alanine transaminase; AST = aspartate aminotransferase; BM = bone marrow; BUN = blood urea nitrogen; CBC= complete blood count; CK = creatinine kinase; CR = complete response; CRP = C reactive protein; CT = computed tomography; D = day; ECG = electrocardiogram; EOT = end of treatment; GGT = gamma-glutamyl transferase; LDH = lactate dehydrogenase; M = month; MRI = magnetic resonance imaging; PT = prothrombin time; PTT = partial thromboplastin time; TSH = thyroid stimulating hormone; W = week.

- a End of treatment is 28-42 days after the first dose of the last cycle. At the discretion of the investigator, a full disease assessment may be performed prior to completion of 6 cycles of therapy if the patient maintains blood counts needed for CR for at least 4 weeks. This interim assessment will include all assessments required at EOT.
- b Only to collect blood component transfusions and hematopoietic growth factors uses.
- c CT or MRI abdomen at 6 and 18 month time points after EOT. Subjects enrolled in Germany will utilize MRI for all radiographic assessments (CT not permissible).
- d This assessment is required 6 months after EOT only for patients in CR or PR.
- e Patients in CR will have a CBC with differential (no peripheral blood smear) monthly from the EOT assessment until the 181D assessment, then every 3 months for 24 months, then every 6 months thereafter. For patients not in CR, repeat CBC with differential (no peripheral blood smear) every 3 months for 24 months after the end of treatment, and every 6 months thereafter.

[REDACTED]

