#### **13.4.2 Safety Assessment**

Safety endpoints include assessment of AEs, SAEs, changes in clinical laboratory evaluations and vital signs. The occurrence of AEs, abnormal laboratory values, and SAEs reported from the first administration of moxetumomab pasudotox through 30 days after last dose of moxetumomab pasudotox will be summarized for all subjects who received any moxetumomab pasudotox. AEs and SAEs will be graded according to the NCI CTCAE V4.0 and described by system organ class and by Medical Dictionary for Regulatory Activities (MedDRA) preferred term, severity, and relationship to moxetumomab pasudotox. Frequency rates will be calculated for each system organ class and MedDRA preferred term.

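### Scheduled adverse event collection can stop up to 6 days before the 30-day safety summary window closes, because the protocol dates end of treatment in two ways

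*Protocol*

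**What the plan says.** Four parts of the protocol bear on when AE collection ends.

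- **Section 7.4.1** (AE collection period): AEs are collected "throughout the treatment period, and 4-6 weeks after the last dose (end of treatment"). The anchor is the last dose, and the text labels that point end of treatment.
- **Section 3.3.4.1 and Table 10-2, footnote a** (timing of the EOT assessment): the section heading reads "All patients 28-42 days after the first day of dosing of prior cycle (end of treatment assessment"), and the footnote reads "End of treatment is 28-42 days after the first dose of the last cycle". The anchor is the first dose of the cycle.
- **Table 10-2, AE row**: a single mark, in the EOT column. No later follow-up visit has one.
- **Section 13.4.2** (safety summary): AEs, SAEs and abnormal laboratory values from the first administration "through 30 days after last dose of moxetumomab pasudotox will be summarized for all subjects" who were treated.

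Section 5.1.1 supplies the link between the two anchors: the drug is given over 30 "minutes on Days 1, 3 and 5 of each 28-day cycle". Section 7.4.2 adds that AEs unresolved at the last AE assessment "are followed up by the investigator for as long as medically indicated, but without further recording in the eCRF".

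**The concern.** Sections 7.4.1 and 3.3.4.1 describe the same assessment but count from different days. Section 13.4.2 then fixes a third window that neither of them guarantees to cover. A site that follows Table 10-2 exactly may hold the EOT visit, make its last scheduled AE enquiry, and leave part of the 30-day window unasked about. The summary would still describe itself as running through 30 days after the last dose.

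At the other end, a later visit within the permitted range collects events that the specified summary does not use.

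The trial is single-arm, so AE incidence is read on its own without a concurrent control. The observation window behind it should be stated once and actually observed.

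**Working it through.** **Inputs**

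- EOT assessment: 28 to 42 days after the first dose of the last cycle (Section 3.3.4.1; Table 10-2, footnote a).
- Dosing days: 1, 3 and 5 (Section 5.1.1).
- Summary window: 30 days after the last dose (Section 13.4.2).
- AE collection as worded in Section 7.4.1: 4-6 weeks, that is 28-42 days, after the last dose.

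**Formulas**

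- Offset = day of the last dose in the final cycle − 1.
- EOT in days after the last dose = (28 to 42) − offset.
- Largest shortfall = 30 − earliest EOT day. Largest excess = latest EOT day − 30.

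**Can the protocol's own figure be reproduced?** Section 7.4.1 puts EOT at 28-42 days after the last dose. After a full final cycle the offset is 5 − 1 = 4, so the scheduled visit falls 28 − 4 = 24 to 42 − 4 = 38 days after the last dose. The figure is not reproduced. Conversely, 28-42 days after a Day 5 dose is 32-46 days after the first dose, not the scheduled 28-42. The two definitions agree only if the final cycle stopped after its Day 1 dose.

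**All readings**

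| Reading | EOT, days after last dose | Largest shortfall against 30 days | Largest excess over 30 days |
|---|---|---|---|
| Last dose Day 5 (full cycle) | 24-38 | 30 − 24 = 6 | 38 − 30 = 8 |
| Last dose Day 3 | 26-40 | 30 − 26 = 4 | 40 − 30 = 10 |
| Last dose Day 1 | 28-42 | 30 − 28 = 2 | 42 − 30 = 12 |
| Section 7.4.1 taken literally | 28-42 | 2 | 12 |

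**Full final cycle, visit by visit.** To reach 30 days after the last dose, the visit must be at least 30 + 4 = 34 days after the first dose. Visits on days 28 to 33 fall 24 to 29 days after the last dose and leave 6 down to 1 days uncovered. A visit on day 34 covers the window exactly. Visits on days 35 to 42 fall 31 to 38 days after the last dose and collect up to 8 days of events beyond the summary.

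Under every reading the permitted range opens before day 30 and closes after it. Only the size changes.

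**The case against.** Several objections have weight.

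- **No sentence says recording stops at the EOT visit.** Section 3.3.1 speaks of continuous monitoring after enrolment, and the mark in Table 10-2 shows a scheduled enquiry, not a cut-off date. This stands, which is why the point is limited to scheduled collection. Section 7.4.2 does, however, presuppose a last AE assessment, and no later one is scheduled.
- **The most important events have their own route.** A reader might infer that rates of hemolytic uremic syndrome (HUS), capillary leak syndrome (CLS) and ocular events are biased downward. The protocol does not support that. SAEs (Section 7.5) and CLS, HUS and ocular events, even if non-serious (Section 7.6.4), must be reported within 24 hours with no stated end date. Section 7.3.3 defines ocular events over the whole course of the study. These rules still depend on the site learning of the event, but they put such events outside the main gap.
- **The loss is easily overstated.** Six of 30 post-dose days is 20%, but the summary window starts at the first dose. For six cycles on schedule it spans 5 × 28 + 4 + 30 = 174 days, so the worst case is 6/174 = 3.4%. It is 6/34 = 18% only if treatment ends after one full cycle. A reader might also infer that 40% of patients are affected, since 6 of the 15 permitted visit days are too early. That would need visits spread evenly over the range, for which the protocol gives no basis. The log for Amendment 6 gives same-weekday restaging as the reason for the 28-42 day range. This makes day 28 foreseeable, but days 35 and 42 fit equally well, and both cover the full 30 days.
- **Late events are not lost.** Collecting past a fixed summary window is not in itself an error, and Section 13.1 provides for data listings. AEs after day 30 leave the specified summary, not the data.
- **Efficacy is untouched.** The primary endpoint and power do not depend on this, and there is no between-arm comparison to distort.

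What remains is the conflict of anchors and a summary window that the scheduled AE collection need not reach.

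**Conclusion.** The point holds in a narrow form. Section 7.4.1 contradicts Section 3.3.4.1 and Table 10-2 on when EOT falls, and neither definition guarantees the 30 days that Section 13.4.2 summarises. After a full final cycle given on schedule, an EOT visit 28-33 days after the first dose leaves 1-6 days without scheduled AE collection. The largest gap is 4 or 2 days if the last dose was on Day 3 or Day 1, and 2 days if Section 7.4.1 is taken literally. AEs arising 31-38 days after the last dose of a full cycle can be collected yet fall outside the summary, though they may still be listed.

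The gap bears mainly on new non-serious AEs that are not of special interest. How many patients would have an early visit, and how many events would be missed, cannot be derived from the protocol; the effect on incidence is probably small. A later analysis plan could list late events, but it could not recover events that were never collected.

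**What to change.** 1. Reconcile Section 7.4.1 with Section 3.3.4.1 and Table 10-2 so that EOT has one anchor throughout.
2. State in Section 7.4.1 and in the AE row of Table 10-2 that AEs are collected through the later of the EOT assessment and 30 days after the last dose, with a telephone contact where EOT comes earlier.
3. State in Section 13.4.2 that the summary covers treatment-emergent events through that same date.

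After a full final cycle, follow-up past the last dose would then run 30 to 38 days. If a uniform window is also wanted, a supplementary table cut at 30 days would give it, and that window would then be fully covered.

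The cost is a wording change, an occasional telephone contact for patients with an early EOT visit, and possibly slightly higher AE counts. Dosing, eligibility and efficacy rules are unaffected.
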